Despite multiple options for colorectal cancer (CRC) screening, including several proven to reduce CRC mortality, population-level participation rates are suboptimal. In 2015, it was estimated that only 62% of Americans aged 50-75 were up to date with screening, which is substantially lower than the 80% by 2018 screening goal set by the National Colorectal Cancer Roundtable and endorsed by the American Society of Gastrointestinal Endoscopy.¹ The US Multi-Society Task Force (USMSTF) recommends colonoscopy and fecal immunochemical testing (FIT) as Tier 1 screening tests,² but barriers to completing these tests have been well-characterized.³ For colonoscopy, patient barriers include an aversion to the bowel preparation process, loss of a workday, and the invasive nature of the procedure. For FIT, the main patient barrier is a reluctance to handle stool samples. Although blood-based tests are not currently recommended in the screening guidelines, they overcome all of these known barriers and may substantially improve adherence to screening. Epi proColon is an FDA-approved blood test that detects methylated Septin9 DNA, which is increased in individuals with CRC. The test is indicated for average-risk individuals who have declined guideline-recommended screening options, such as colonoscopy and FIT. Guidelines suggest that patients who decline these Tier 1 options should be offered Tier 2 or 3 options such as sigmoidoscopy, stool-DNA, CT colonography, and capsule colonoscopy. However, since these lower-tier tests face the same patient barriers as the Tier 1 tests and are less widely available, individuals who have declined both colonoscopy and FIT constitute the *de facto* target population for the blood test. Studies have shown that patients who are offered a choice between the blood test and FIT prefer and have higher compliance to the blood test,^{4,5} but it is unknown what proportion of "screen-resistant" patients who have declined *both* colonoscopy and FIT will accept the blood test. This is the crucial question that will determine the potential role of the blood test in the CRC screening landscape.

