
Our prior work has shown that adherence to fecal testing declines rapidly with successive rounds of screening,¹² which highlights the potential of a blood-based test with high-compliance for capturing non-adherent individuals. The performance of the Septin9 blood test was first studied in 7941 asymptomatic individuals, which found an age-standardized 48% sensitivity and 92% specificity for CRC.¹³ These results were based on an assay that defined test positivity as one of two samples with a positive result. A subsequent study has shown that redefining test positivity as one of three samples with a positive result yielded 68% sensitivity and 79% specificity for CRC.¹⁴ The current FDA-approved Epi proColon assay uses three samples. In a trial that compared the blood test to FIT in individuals who were either recently diagnosed with

PROTOCOL TITLE: Assessing the effect of offering a blood-based colorectal cancer screening test

CRC or were undergoing screening colonoscopy, the blood test was found to be non-inferior to FIT with respect to sensitivity (73% vs. 68%) for CRC but had lower specificity (82% vs. 97%).¹⁵ Two studies have evaluated uptake of the blood test compared to FIT. In a German study of 109 individuals who refused screening colonoscopy, 83% chose the blood test and 15% chose FIT. In a multi-center randomized controlled trial conducted in the US, patients who were overdue for screening were assigned to either the blood test or FIT. Test completion rate was 99.5% for the blood test and 88% for FIT. Of the 30 individuals who had a positive blood test, 20 (67%) scheduled or completed a diagnostic colonoscopy within 3 months.

4) Inclusion and Exclusion Criteria

Inclusion criteria (based on review of the electronic health record):

- Age 50-75
- Declined CRC screening (both colonoscopy and FIT) in the previous 6 months, which must be documented in the electronic health record

Exclusion criteria (based on review of the electronic health record data and self-reported questionnaire data):

- Personal history of colonic adenomas (including sessile serrated adenomas), proximal hyperplastic polyps, CRC, inflammatory bowel disease, or hereditary gastrointestinal cancer syndrome
- First degree relative with CRC diagnosed at <60 years of age; family history of hereditary gastrointestinal cancer syndromes.

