Primary outcome: Screening rate in the intervention group vs. control group after 6 months.

Secondary outcomes:

A) Complete screening rate in both groups, which is defined as completion of the entire screening strategy. For colonoscopy, this requires cecal intubation and an adequate bowel preparation. For individuals who took Septin9 and FIT, positive results must be followed by a colonoscopy with cecal intubation and adequate bowel preparation.

B) Among individuals in the intervention group who had a positive blood test, proportion who completed a follow-up colonoscopy within 6 months.

C) Endoscopic and pathologic findings among individuals in the intervention group who had a diagnostic colonoscopy.

Aim #2: *To survey screen-resistant patients to understand their beliefs and attitudes about CRC screening and testing options.* Both intervention and controls groups will be invited to complete a brief questionnaire. Questionnaire questions are shown in the Table and are adapted from a previous study that offered both the blood test and FIT to patients who had refused screening colonoscopy.⁴ All response options will be presented in a multiple-choice format. The full questionnaire is shown in the Appendix.

Primary outcome: Demographic and health-related predictors of accepting the blood test in the intervention group.

Secondary outcomes:

A) Proportion of both groups who answered that they would be willing to take a blood test for colorectal cancer screening

B) The most commonly cited advantages of a blood test compared to colonoscopy and stool test in both groups

C) The most commonly cited reasons for not taking the blood test in the intervention group. In an exploratory analysis, we will stratify results by race/ethnicity, self-reported health, frequency of healthcare access, and self-perceived risk of CRC.

Table. Select Questionnaire Questions

Demographics
What is your age?
What is your race?
What is your ethnicity?
Health status and medical history
How would you rate your overall health?
How many visits have you had with your primary care doctor in the past year?
What do you think is your own risk of getting colorectal cancer?
Colorectal cancer testing
Have you ever had a colonoscopy? If so, when?
Have you ever had a stool-based test? If so, when?

PROTOCOL TITLE: Assessing the effect of offering a blood-based colorectal cancer screening test

Why did you decide not to do a colonoscopy when offered in the past 6 months?

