The proposed study is a randomized controlled trial that will 1) assess the uptake of a CRC screening blood test among patients who have declined both colonoscopy and FIT in the previous 6 months, including diagnostic evaluation of positive results and 2) survey patients about their beliefs and attitudes regarding CRC screening and testing options. All participants will be primary care patients at the VA NY Harbor Health Care System. Based on a recent internal audit, there were 1502 patients who had at least one primary care visit from August 2016 through August 2017 and were not up to date with CRC screening. Up to date CRC screening is defined as either 1) a colonoscopy within the past 10 years or 2) FIT within the past year. We will perform an updated CRC screening audit at the beginning of the study to obtain the entire pool of eligible patients who are not up to date with screening. Eligible patients will then be randomized 1:1 to either an intervention group or a control group. All patients will receive a letter noting that they are not up to date on screening and encouraging them to contact a study number if they choose to screen with colonoscopy or FIT. Patients who call will speak to a research assistant who is trained in patient navigation and can facilitate referrals for colonoscopy or FIT. Following the sequential testing approach, letters addressed to the intervention group will also include an option to participate in the blood test, with instructions to call the study number to schedule the blood draw. In addition to the letter, both groups will also receive a follow-up telephone call that reiterates information in the letter. The research assistant will make and receive all calls using a standard script. All patients will also be asked to complete a questionnaire about their beliefs and attitudes regarding CRC screening (see Appendix). The questionnaire will be mailed with the invitation letter and will also be administered over the telephone by the research assistant. The study team will notify patients and their primary care physicians of blood test results and will facilitate a colonoscopy referral for those with positive tests. Primary care physicians will not be asked to notify the patients or make the colonoscopy referral because most will not have adequate knowledge of the Septin9 test to provide appropriate patient education.

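### The exclusions admit patients with an old positive stool test never followed by colonoscopy, or symptoms already referred for work-up, and secondary outcome A can count them as completely screened

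*Combined protocol and SAP*

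**What the plan says.** The protocol's opening section states the intended population: "The test is indicated for average-risk individuals who have declined guideline-recommended screening options". The end of section 3 (Background) adds that the trial will measure the test's effect in the clinical situation for which it is indicated.

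Section 4 requires age 50-75 and "Declined CRC screening (both colonoscopy and FIT) in the previous 6 months, which must be documented in the electronic health record". Its exclusions are:

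- "Personal history of colonic adenomas (including sessile serrated adenomas), proximal hyperplastic polyps, CRC, inflammatory bowel disease, or hereditary gastrointestinal cancer syndrome"
- a parent, sibling or child found to have CRC before age 60, or a hereditary GI cancer syndrome in the family
- severe comorbidity with limited life expectancy, and vulnerable groups.

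Section 9 sets the rule for the audit that forms the pool: "Up to date CRC screening is defined as either 1) a colonoscopy within the past 10 years or 2) FIT within the past year". The FIT result plays no part in it.

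Section 8, Aim 1, secondary outcome A defines complete screening. For people who took the blood test or FIT, "positive results must be followed by a colonoscopy with cecal intubation and adequate bowel preparation". Results obtained before the study are not mentioned.

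**The concern.** Consider a 62-year-old with a positive FIT 14 months ago and no colonoscopy since, who declined both colonoscopy and FIT 3 months ago. The FIT is more than a year old, so the patient is not up to date. Both inclusion criteria are met and no exclusion applies. In the intervention arm the patient is offered the blood test. If it is negative, outcome A requires nothing further and the patient counts as completely screened. A negative repeat FIT does the same in either arm. The same eligibility gap exists for a patient whose record shows lower-GI symptoms already referred for diagnostic colonoscopy.

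Three things are at stake:

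- Applicability: the result is meant to describe average-risk decliners, but the sample may include people who already have a reason for diagnostic work-up.
- Meaning of the secondary outcomes: outcome A credits a completed strategy to someone with an earlier positive left unresolved, and outcome C (endoscopic and pathologic findings) mixes such people with average-risk ones.
- False reassurance: a negative screening result is given to a person with an open finding.

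**Working it through.** **Eligibility and endpoint, taken in order**

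1. Audit (section 9): a FIT older than one year leaves the patient not up to date, whatever its result. A FIT within the past year, even if positive, counts as up to date and keeps the patient out. The gap therefore concerns older positives.
2. Inclusion (section 4): a documented decline of both tests in the previous 6 months can be met by such a patient.
3. Exclusion (section 4): no item names a prior positive stool test, symptoms or signs.
4. Later filter: section 4 says exclusions also draw on self-reported questionnaire data. But section 9 mails the questionnaire with the invitation letter, which follows randomisation, and section 23 calls it anonymous. Item 14a asks how long ago the last stool test was, not what it showed. The opening items of the questionnaire were not available for this check and may ask about symptoms or history. Even so, section 4 would still list no matching exclusion.
5. Endpoint (section 8, outcome A): colonoscopy is required only after a positive test among those taken; earlier results are not addressed.

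**The plan's own sample size, which is not in dispute**

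Inputs from section 11: 50% in the intervention group, a 15-point difference (control 35% implied), alpha 0.05 (taken as two-sided), power 80%.

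n = [1.960·√(2p̄(1−p̄)) + 0.8416·√(p₁(1−p₁) + p₂(1−p₂))]² / (p₁−p₂)², with p₁ = 0.50, p₂ = 0.35, p̄ = 0.425

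= [1.960·√0.48875 + 0.8416·√0.4775]² / 0.0225 = (1.3702 + 0.5816)² / 0.0225 = 169.3, rounded up to **170**, as stated. Power is 80.2% at 170 and 82.4% at 180 per group.

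**Size of the effect on outcome A**

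The documents give no prevalence, so the affected share f is an assumption, covering both kinds of patient together. Other inputs: 180 intervention patients, 50% uptake (section 11), and 79% specificity for the three-sample assay (section 3). Affected patients are assumed to accept the test at the general rate and to be free of cancer.

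Patients counted complete on a negative blood test = 180 × f × 0.50 × 0.79. Percentage points = that count / 180 × 100.

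| f (assumed) | Affected in arm | Tested | Negative, counted complete | Points of arm's rate |
|---|---|---|---|---|
| 1% | 1.8 | 0.9 | 0.7 | 0.4 |
| 2% | 3.6 | 1.8 | 1.4 | 0.8 |
| 5% | 9.0 | 4.5 | 3.6 | 2.0 |
| 10% | 18.0 | 9.0 | 7.1 | 4.0 |

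At the 82% specificity also cited in section 3, the range is 0.4 to 4.1 points. For any cancers among those tested, the sensitivities of 68% and 73% in section 3 imply that 100 − 73 = 27% to 100 − 68 = 32% would test negative. No cancer prevalence is given, so this cannot be turned into a count.

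**When the exclusion is applied**

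Applied before randomisation, it leaves the requirement at 170 per group and costs no power if the pool suffices. Applied after randomisation without replacement, it leaves about 178, 176, 171 and 162 per arm at the four shares, with power 82.0%, 81.6%, 80.4% and 78.2%, before any drop-out.

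**The case against.** The strongest reply is that this is a narrow gap in wording. The personal- and family-history exclusions are a recognisable working version of average risk, a term the protocol does not define. Inclusion concerns declined screening, and clinicians may record a refusal after a positive FIT or for symptoms as a declined diagnostic referral instead. Randomisation should balance such patients between arms, and section 11 plans only descriptive statistics for clinical outcomes in those who took the blood test. Much of this stands: the failure is partial and the numbers may be small. But no rule ensures the recording practice, and balance does not change who is enrolled or what outcome A counts.

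A reader might also infer more than the documents support:

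- *That the protocol restricts the test to asymptomatic people.* The only use of that word here describes a cited performance study: "The performance of the Septin9 blood test was first studied in 7941 asymptomatic individuals". The stated indication is average risk.
- *That eligibility and outcome A contradict each other.* Outcome A is silent on pre-study results; the two are unreconciled, not opposed.
- *That a pool of colonoscopy refusers is enriched for old positive FITs.* These patients once accepted FIT, and inclusion selects for recent FIT refusal, which could deplete the group as easily as enrich it.
- *That outcome B would rise.* B is follow-up colonoscopy among blood-test positives. People who already went without colonoscopy after a positive FIT could lower it.
- *That the same share of all 360 patients measures the problem.* Only the 180 in the intervention arm can take the blood test, and half are expected to.

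**Conclusion.** The point holds as a gap in eligibility and in one secondary definition. Followed as written, the plan can enrol a patient with an unresolved positive stool test, or with symptoms already referred for work-up, and can count that patient as completely screened on a negative study test.

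The size is about 0.7 to 7.1 patients, or 0.4 to 4.0 points of the intervention arm's complete screening rate. This rests entirely on an assumed share of 1% to 10%, the plan's 50% uptake and 79% specificity. The net effect on the between-arm difference is smaller, because control patients can reach the same status by a negative repeat FIT. It need not vanish, because the blood test is an extra route in one arm only.

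A reader might conclude that the primary comparison is biased. The documents do not show that: allocation is randomised 1:1, so such patients should be balanced. The issue is applicability, the meaning of outcomes A and C, and false reassurance.

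**What to change.** Reconcile the stated indication, the section 4 exclusions, the section 9 'up to date' definition and outcome A. The direct way is to add two items to the record-based exclusions, applied before randomisation:

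1. a documented positive stool test with no completed colonoscopy since;
2. documented lower-GI symptoms or signs already referred for diagnostic colonoscopy.

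At minimum, outcome A should state that a patient with an unresolved earlier positive stool test is not complete without a colonoscopy meeting the plan's existing standard, in either arm.

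The cost is two more items in a chart review already required by section 4. The sample size does not change. The downside is a somewhat smaller pool, which must be checked: the 1502 patients in the section 9 audit were not up to date, but had not been filtered for documented refusal of both tests or for the exclusions. They cannot be taken as the number available for 360 places.

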What would make you change your mind and get a colonoscopy?
Why did you decide not to do a stool test (fecal immunochemical test/FIT) when offered in the past 6 months?
What would make you change your mind and take a stool test?
Why did you decide to take a blood test?
What are the advantages of a blood test compared to colonoscopy and stool test?
Why did you decide not to take a blood test?
What would make you change your mind and take a blood test?

9) Procedures Involved

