Aim 1: Two prior studies that have measured uptake of the Septin9 blood test have found very high rates of 84% and 99%, respectively.^{4,5} The study that found 84% uptake involved patients who had previously declined colonoscopy and were subsequently given a choice between the blood test and FIT. Since our study population has previously declined both colonoscopy and FIT, their uptake of the blood test will likely be lower. We estimate that uptake in our population will be 50% and will power our study to detect a 15% absolute difference in screening rate. With alpha = 0.05 and 80% power, the required sample size in each group is 170. To account for drop-out, we will include 180 patients in each group.

Aim 2: Assuming a 50% uptake in the intervention group of 170 individuals, there will be an estimated 85 individuals who take the blood test. We will select variables with the strongest association with blood test completion on bivariate analysis, which will be entered into the final multivariable logistic regression model. The number of variables in the final model will be limited to ensure that there are at least 10 events per variable, which is the conventional minimum standard to preserve model validity.¹⁶

12) Provisions to Monitor the Data to Ensure the Safety of Subjects

We believe this study poses no more than Minimal Risk to study participants, and therefore there are no plans to establish a data monitoring committee. However, any unexpected adverse events will be reported immediately to the PI, who will report to the IRB on an ad-hoc basis.

PROTOCOL TITLE: Assessing the effect of offering a blood-based colorectal cancer screening test

13) Withdrawal of Subjects

There are no anticipated circumstances under which subjects will be withdrawn from the research without their consent. Participants may choose to withdraw from the study at any point by giving notification to the study team. Patients who withdraw from the study will no longer be tracked in the electronic medical record after the time of withdrawal.

14) Risks to Subjects

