Patients will be informed of the potential risks as part of the informed consent process. All efforts will be made to ensure patient confidentiality and assurance of HIPAA compliance. Participant data will be de-identified using a protocol-specific unique code that will be used for all further data management. A list matching the patient medical record number to the protocol specific unique code will be maintained in a password-protected file in the PI's private drive on the VA network. There will be no data entry or interpretation outside of the VA NY Harbor Health Care System. The names of the patients will not be revealed in written reports or publications detailing the research findings.

21) Provisions to Protect the Privacy Interests of Subjects

The study team will take every possible precaution to protect the privacy of study participants. Only study team members who have been trained by the PI will be allowed to access patient data. Participants data will be de-identified for analysis and only aggregate data will be presented for publication. In addition, participants will not be required to answer any questionnaire question that may make him/her not at ease.

22) Compensation for Research-Related Injury

N/A

23) Consent Process

We are requesting waiver of HIPAA and informed consent for the purpose of screening patients who are eligible for participating in the study. For the control arm, we are requesting waiver of HIPAA and informed consent to access their medical record and determine whether they undergo a colonoscopy for FIT within 6 months of the initial invitation letter. For participants in the intervention arm who elect to undergo the blood test, written informed consent and HIPAA authorization will be obtained onsite prior to phlebotomy. All patients will also be invited to participate in a short anonymous questionnaire by mail and if needed, by phone. A one-page description of the questionnaire and how to contact the research team will be provided in the mailing and reiterated in the phone call. However, we are requesting waiver of documentation of consent for the anonymous questionnaire.

24) Drugs or Devices

N/A

PROTOCOL TITLE: Assessing the effect of offering a blood-based colorectal cancer screening test

REFERENCES

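### If the Aim 2 primary model draws its predictors from the voluntary questionnaire, it covers responders only, while the sample size reasoning counts every intervention patient; the health record is a better source

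*Combined protocol and SAP*

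**What the plan says.** Section 8, Aim 2, defines the endpoint: "Primary outcome: Demographic and health-related predictors of accepting the blood test in the intervention group". Section 11 (Data Analysis) assigns it a multivariable logistic regression. The table in section 8 lists age, race, ethnicity, self-rated health, primary care visits in the past year and perceived colorectal cancer risk as questionnaire questions.

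The questionnaire is voluntary: "Both intervention and controls groups will be invited to complete a brief questionnaire". Under section 21, "participants will not be required to answer any questionnaire question that may make him/her not at ease". On delivery, section 9 states: "The questionnaire will be mailed with the invitation letter and will also be administered over the telephone by the research assistant". Section 23 puts it as: "All patients will also be invited to participate in a short anonymous questionnaire by mail and if needed, by phone". The available text gives no return deadline and no rule placing completion before the blood draw or the result. The opening items of the Appendix questionnaire are not in the text reviewed, so an instruction or date field there cannot be excluded.

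Section 11 also says that study data come from the electronic medical record, without naming the model variables taken from it. The sample size paragraph for Aim 2 reads: "Assuming a 50% uptake in the intervention group of 170 individuals, there will be an estimated 85 individuals who take the blood test". It requires ten events for each variable and makes no allowance for questionnaire non-response.

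**The concern.** Two things follow if the form supplies the predictors.

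First, a patient who returns no form has no predictor values and drops out of the model. Taking the blood test requires contact with the study: a call to schedule, then a visit for consent and phlebotomy. Anyone who never responds to the letter or the calls is therefore a non-taker, and is also unlikely to return a form. The non-taker class may be depleted more than the taker class, which reduces precision and the number of variables the model can carry. If response among non-takers also varies with a predictor, that predictor's odds ratio is biased.

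Second, perceived risk and self-rated health can change. With no visible cut-off, a taker could answer after deciding, or after hearing the result. The answer would then partly reflect the event it is meant to predict.

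Neither problem is solved by linking forms to patients. Fully linked forms would still cover responders only and could still be completed late.

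**Working it through.** **1. The plan's own figure.** Inputs from section 11 (Sample Size Calculations): 170 intervention patients, 50% uptake, ten events per variable.
- Takers: 0.50 × 170 = 85. This reproduces the plan. Non-takers: 170 − 85 = 85.
- Variables supported: 85 / 10 = 8.5, so 8. The plan does not state the 8; it follows from its rule.

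**2. Effect of non-response.** The documents give no response rates, so those below are assumptions. Responders in each class = 85 × response rate. Variables supported = smaller class / 10, rounded down.

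| Taker response | Non-taker response | Takers left | Non-takers left | Takers' share of responders | Variables |
|---|---|---|---|---|---|
| 100% | 100% | 85 | 85 | 50% | 8 |
| 80% | 80% | 68 | 68 | 50% | 6 |
| 80% | 70% | 68 | 59.5 | 53% | 5 |
| 80% | 50% | 68 | 42.5 | 62% | 4 |
| 80% | 30% | 68 | 25.5 | 73% | 2 |
| 80% | 20% | 68 | 17 | 80% | 1 |

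In the 80%/30% row, for example, 85 × 0.30 = 25.5 and 68 / (68 + 25.5) = 73%. If takers are read literally as the events, that row would allow 68 / 10, so 6 variables, against about 26 non-takers. The smaller class is the limiting one.

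**3. When the odds ratio is biased.** For a binary predictor with true odds ratio 1, the odds ratio among responders is (taker response with trait / taker response without) / (non-taker response with trait / non-taker response without).
- Response depends on uptake only (takers 80%, non-takers 30%, trait irrelevant): (0.8/0.8) / (0.3/0.3) = 1.0. There is no bias.
- Non-takers in good health respond at 20% and those in poor health at 40%, takers at 80% in both (assumed): (0.8/0.8) / (0.2/0.4) = 2.0.
- With the non-taker rates reversed: (0.8/0.8) / (0.4/0.2) = 0.5. The direction is not predictable.

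**4. Late answers.** Assume a changeable trait with 50% prevalence and true odds ratio 1, and let a fraction m of takers without the trait report it because they answer late. The trait's odds among takers become (0.5 + 0.5m) / (0.5 − 0.5m), against odds of 1 among non-takers.
- m = 10%: 0.55 / 0.45 = 1.22
- m = 20%: 0.60 / 0.40 = 1.50
- m = 30%: 0.65 / 0.35 = 1.86

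This mechanism cannot affect age, race or ethnicity, and past-year visits are little exposed.

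**The case against.** The case for leaving the plan alone has substance.

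- **Source of predictors.** The plan does not say that every model variable comes from the form, and the record is a stated data source. A reader might infer that perceived risk is certain to be a predictor in the model. The text does not say so: perceived risk and self-rated health are named explicitly only as strata for the secondary and exploratory results. They do sit in the health block of the questionnaire table, so their use is plausible.
- **Timing.** The form travels with the invitation, before a patient can call, consent and be drawn, and the assay is run off-site before results are given. The full questionnaire in the Appendix asks about the blood test conditionally. A reader might infer that forms are normally completed after the result; the documents do not support that. Late completion remains possible, and the section 8 table words one item as "Why did you decide to take a blood test", which presupposes a decision already made.
- **Who responds.** A reader might also infer that the data will come mainly from acceptors. That is a risk, not a documented fact: both groups receive the form by mail, and the research assistant also administers it by telephone, which reaches some non-takers.
- **The variable rule adapts.** The plan limits the number of variables to respect its ratio, so non-response costs precision and model size rather than breaking the rule, provided the count is made on the smaller class among responders.
- **Scope.** The randomised Aim 1 comparison is untouched.

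These points narrow the concern. They do not supply a predictor source, a completion window or an allowance for non-response.

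**Conclusion.** The point holds conditionally. If the Aim 2 primary model uses the questionnaire, it is a responder-only model, and the 170 patients and 85 takers in the sample size paragraph overstate the data available to it. Under assumed taker response of 80%, non-taker response between 70% and 30% leaves about 60 to 26 non-takers, supporting 5 to 2 variables instead of 8. These are illustrations, not forecasts.

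Loss of precision follows from low non-taker response alone. Bias does not: it needs response to depend on the predictor as well as on uptake, and the documents neither show nor exclude that. A statement that the odds ratios will be biased because acceptors are over-represented would go too far. Late measurement is a secondary risk confined mainly to perceived risk and self-rated health.

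This is a cheap improvement to an association analysis, and it avoids the problem for most of the predictors.

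**What to change.** 1. **Primary Aim 2 model.** State that age, race/ethnicity, primary care visits in the past year and comorbidity are taken from the health record as of the randomisation date, for every intervention patient. The record is already reviewed for eligibility. This restores the denominator assumed in the sample size paragraph.
2. **Form-only items.** Move self-rated health and perceived risk to a secondary responder-only model, reported as associations.
3. **Timing.** Apply one completion window, counted from the mailing date, to takers and non-takers alike. A cut-off at the blood draw would not serve, because non-takers have no draw and the filter would remove takers only. Add a sensitivity analysis that excludes forms completed after result notification. It also removes only takers, so read it as a check on late answers and not as the main result.
4. **Reporting.** Give questionnaire response by taker status, and count variables against the smaller outcome class.

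**Cost.** Wording in sections 8 and 11, and a few more fields in the record review. The form-only items leave the primary model. Item 3 needs dated, linkable forms, which must be reconciled with the anonymous questionnaire in section 23. That section describes record access for eligibility screening and control outcomes, and consent for takers, but does not name intervention-arm decliners; the waiver wording may need to be extended to them.
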